**Table 10.1-1: Simon 2-stage (Optimal) Design Considerations**

Track	Historical ORR/ Target ORR	Stage 1 Responders/Stage 1 n		Stage 2 Responders/Total n		Expected n with Historical ORR	Expected n with Target ORR
		Consider Futility	Go to Stage 2	Consider Futility	Consider Efficacy		
1	20%/40%	≤ 4/19	≥ 5/19	≤ 15/54	≥ 16/54	30.4	51.6
2	5%/20%	≤ 1/21	≥ 2/21	≤ 4/41	≥ 5/41	26.6	39.8

Note: Numbers of responses serve as a guideline; however, the totality of efficacy data will be considered when making decisions to terminate or continue an arm.

The Track 1 Simon 2-stage (optimal) design assumes a historical response rate of 20% and a target response rate of 40%, based on the observed response rate of approximately 24% for the nivolumab in combination with ipilimumab and approximately 12% for nivolumab monotherapy participants in Study CA209032. A false positive rate of 5% and power of 90% are used.

Because there is very little data available on participants with prior anti-PD-1, anti-PD-L1, or anti CTLA-4 treatment, the Track 2 design is not based on an observed historical response rate. Rather, the assumption is made that a response rate below 5% would not be worth further study and that a target response rate of 20% would be worth pursuing in this population. A false positive rate of 5% and power of 90% are used.

[figure not shown]
With regard to sample size, participants who are re-randomized to a different study treatment in Track 2 will be counted once for each randomization; participants who are retreated within the same study treatment arm will only be counted once.

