Combining immunotherapeutic agents with different mechanisms of action offers the possibility of further benefit, as noted with the combination of nivolumab and ipilimumab now approved in the US for the treatment of patients with metastatic melanoma. In Study CA209032 (“A Phase 1/2, Open-label Study of Nivolumab Monotherapy or Nivolumab combined with Ipilimumab in Subjects with Advanced or Metastatic Solid Tumors,” NCT01928394), participants with GC or GEJ were treated with nivolumab 1 mg/kg in combination with ipilimumab 3 mg/kg or nivolumab monotherapy. Participants treated with nivolumab 1 mg/kg in combination with ipilimumab 3 mg/kg had an objective response rate (ORR) of 24% and 12-month progression-free survival rate (PFSR) of 17%. This was greater than the ORR and 12-month PFSR in participants treated with nivolumab monotherapy, who had an ORR of 12% and a PFSR of 8%. This study treatment combination regimen has also been chosen for use in a Phase 3 registration study in first-line GC. Hence, nivolumab 1 mg/kg in combination with ipilimumab 3 mg/kg has been chosen as the control treatment in FRACTION-Gastric Cancer Sub-Protocol A. (Further details are described in the FRACTION-Gastric Cancer Sub-Protocol A). These data also suggest the potential for other combinations to bring additional benefit to participants with GC and GEJ.

This document will serve as the Master Protocol for the FRACTION-Gastric Cancer study (FRACTION-Gastric Cancer; CA018003). As described above, novel study treatment combinations and/or additional controls will be appended as FRACTION-Gastric Cancer Sub-Protocols. These FRACTION-Gastric Cancer Sub Protocols- will evaluate the safety profile, tolerability, preliminary efficacy, PK, and pharmacodynamics of novel study treatment combinations in participants with advanced GC. The initial control treatment in the FRACTION-Gastric Cancer study will be nivolumab in combination with ipilimumab followed by nivolumab monotherapy, similar to what has been administered in Study CA209032 as described above.

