**Table 4-1: Objectives and Endpoints**

Objectives	Endpoints

Primary
 
 
To assess the efficacy (ORR, DOR, and PFSR at 24 weeks) of each FRACTION-Gastric Cancer study treatment combination (relative to nivolumab in combination with ipilimumab, when applicable) in participants with advanced GC and/or EC
 
	
 
ORR, defined as the proportion of all treated participants with a BOR of CR or PR as assessed per RECIST v1.1 by investigator, median DOR, and PFSR at 24 weeks
 

Secondary
 
 
To investigate additional safety and tolerability of each FRACTION-Gastric Cancer study treatment combination in participants with advanced GC and/or EC
 
	
 
Incidence of AEs, SAEs, and AEs leading to discontinuation, deaths, and clinical laboratory test abnormalities
 

Tertiary/Exploratory
 
 
To assess the pharmacodynamic effects as a function of exposure, by evaluation of select biomarkers [REDACTED]
 
To explore potential associations between anti-tumor activity or safety and select biomarker measures [REDACTED]
 
To evaluate the PK of each IP component
 
To evaluate the immunogenicity of each IP, when applicable
 
To assess the OS in treated participants
 
To evaluate disease-related symptom improvement, as measured by the GaCS of the FACT-Ga and the ECS of the FACT-E in treated participants
 
To evaluate general health, functional status, and utility for health using the EQ-5D-3L in treated participants
 
	
 
Summary measures of change (or % change) from baseline or baseline level biomarker measurements [REDACTED]
 
Correlation (or similar appropriate measure of association) of biomarker measure [REDACTED]
 
Summary measures of PK parameters from serum concentration
 
Incidence of ADAs
 
OS rate at certain time points
 
Summary measures of EQ-5D-3L index and VAS scores, GaCS scores, and/or ECS scores, and corresponding change from baselines for each score
 

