### **2) Type of Participant and Target Disease Characteristics**

- a) All participants must have inoperable, advanced, or metastatic EC, GC or GEJ carcinoma and have histologically confirmed predominant adenocarcinoma and/or squamous carcinoma. The documentation of GEJ involvement can include biopsy, endoscopy, or imaging.
- b) Participants with human epidermal growth factor receptor 2 (HER2) overexpressing tumor who progress after trastuzumab (or are ineligible for or unwilling to be treated with trastuzumab) are eligible to be enrolled.
- c) Prior adjuvant or neoadjuvant chemotherapy, radiotherapy, and/or chemoradiotherapy are permitted, as long as the last administration of the last regimen (whichever was given last) occurred at least 4 weeks prior to randomization.
- d) Participants must have an Eastern Cooperative Oncology Group performance status  $\leq 1$  (see [Appendix 7](#)).
- e) Track-specific eligibility criteria
  - i) Track 1: anti-PD-1, anti-PD-L1, and anti-CTLA-4 treatment-naïve participants
    - (1).Participants must not have received any anti-PD-1, anti-PD-L1, or anti-CTLA-4 treatment prior to this study. Participants previously treated with agents other than anti-PD-1, anti-PD-L1, or anti-CTLA-4 are eligible for Track 1.
    - (2).Participants may have been offered platinum-based chemotherapy for progressive or recurrent disease.
      - a. The platinum-based chemotherapy may have been in the adjuvant, neoadjuvant, or recurrent setting.
    - (3).Not Applicable per Amendment 02.
    - (4).Not Applicable per Amendment 03.

- (5). All participants must consent to the acquisition of fresh pre- and on-treatment tumor biopsies for performance of correlative biomarker studies. Archival specimens may not be substituted for fresh baseline specimens but can be submitted to help understand the evolution of the tumor (ie, PD-L1 expression changes over time) for performance of correlative studies. Participants who either do not consent to a pre-treatment tumor biopsy or do not have accessible lesions are not eligible. An adequate baseline tumor biopsy as determined by a central laboratory pathologist must be obtained prior to randomization. If fresh biopsy is not clinically feasible or safe, the option of archival tissue can be discussed with BMS if the biopsy was obtained within 90 days of study enrollment and there was no intervening systemic anticancer or IO therapy.

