Each participant who is randomized will be assigned a unique randomization number. This is not the primary identifier for the participant, but is used for the randomization schedule. The primary identifier will be the PID described above, for use on the case report form (CRF) and source documents. A participant being re-randomized in Track 2 will be assigned a different randomization number but will retain the same PID. Randomization numbers will be assigned using a Central Randomization System in the order in which participants qualify for study treatment, not in the order of study enrollment. Randomization ratios within each track will be specified in each FRACTION-Gastric Cancer Sub-Protocol. If, within a given track, study treatment arms from more than 1 FRACTION-Gastric Cancer Sub-Protocol within the FRACTION-Gastric Cancer Master Protocol are simultaneously open to enrollment, then a new participant could be assigned to any of the open study treatment arms. In Track 1, participants will be randomized to newly added study treatment arms/study treatments (through FRACTION-Gastric Cancer Sub-Protocols) in a ratio specified in each new FRACTION-Gastric Cancer Sub-Protocol. New randomization schedules for new FRACTION-Gastric Cancer Sub-Protocols will be generated. If accrual for current FRACTION-Gastric Cancer Sub-Protocols is still ongoing, participants will be allocated to the existing randomization schedule or new randomization schedule based on a pre-specified allocation ratio. Details of allocation ratio will be specified in the new FRACTION-Gastric Cancer Sub-Protocol. In Track 2, participants will be randomized to existing study treatment arm/study treatments and newly added study treatment arm/study treatments with equal probability.

Pre-specified study treatment arm caps (according to Simon 2-stage [optimal] design) will be utilized to control the accrual for each study treatment combination arm under different tracks (Tracks 1 and 2). The cap for the nivolumab in combination with ipilimumab control arm under Track 1 will be set equal to the largest cap among its corresponding experimental arms. In the event that 1 or more participants go off study without being evaluable for response (ie, with no post-baseline tumor measurements and no evidence of clinical progression or death due to disease progression), the enrollment cap for that study treatment arm may be correspondingly raised if

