### 10.1.1 Track 1 - Anti-PD-1, Anti-PD-L1, and Anti-CTLA-4 Treatment-naïve Participants

As shown in Table 10.1-1, a minimum of 19 participants in each study treatment combination arm will be treated in Stage 1 for an initial evaluation of efficacy. If the total number of responses observed in Stage 1 is  $\leq 4/19$ , the study treatment combination arm would likely not be considered efficacious; otherwise, enrollment to Stage 2 will continue, and an additional 35 participants will be treated. If the total number of responses at the end of Stage 2 is  $\leq 15/54$ , the study treatment combination arm will be terminated for futility; if there are more than 15 responses observed at the end of Stage 2, the study treatment combination arm may be carried on for further treatment development. The totality of efficacy data and response profile for each combination arm will be considered when making decisions to terminate or continue an arm.

The operating characteristics of this Simon 2-stage (optimal) design are provided in Figure 10.1.1-1. With the stopping boundaries as shown in Table 10.1-1, if the study treatment combination arm has an ORR no better than the historical control at 20%, then there is a 95% overall chance of stopping for futility, with a 67% chance of stopping at Stage 1; there is a 5% false positive rate. If the study treatment combination arm has an ORR equal to the target of 40%, then there is a 90% chance of declaring efficacy after Stage 2, whereas if the true ORR is 25%, 30%, or 35%, the power would be 21%, 49%, or 75%, respectively.

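### Does a Track 1 null ORR of 20% misstate the 5% false-positive rate, given that the control regimen's quoted ORR is about 24%?

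*Combined protocol and SAP*

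**What the plan says.** Under Table 10.1-1 (Section 10.1) the Track 1 design "assumes a historical response rate of 20% and a target response rate of 40%, based on the observed response rate of approximately 24" percent for nivolumab plus ipilimumab and roughly 12% for nivolumab monotherapy in Study CA209032. Section 3.2.1 reports the same result: "Participants treated with nivolumab 1 mg/kg in combination with ipilimumab 3 mg/kg had an objective response rate (ORR) of 24" percent. The Master Protocol does not say how 20% was reached from 24% and 12%.

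Section 10.1.1 ties the operating characteristics to that null: "if the study treatment combination arm has an ORR no better than the historical control at 20%, then there is a 95% overall chance". The chance meant is that of ending in futility; beside it the section puts 67% for a Stage 1 stop and 5% for a false positive. For true rates between null and target it adds: "whereas if the true ORR is 25%, 30%, or 35%, the power would be 21%, 49%, or 75%, respectively".

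Three other places bear on the point:

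- Section 7.2 identifies the concurrent control and ties its size to the experimental arms: "The cap for the nivolumab in combination with ipilimumab control arm under Track 1 will be set equal to the largest cap".
- The primary objective in Table 4-1 concerns the efficacy of each "study treatment combination (relative to nivolumab in combination with ipilimumab, when applicable").
- The note to Table 10.1-1 makes the boundary non-binding: "Numbers of responses serve as a guideline; however, the totality of efficacy data will be considered" in decisions to stop or continue an arm.

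**The concern.** The phrase about the historical control carries the concern. The Track 1 control arm is nivolumab plus ipilimumab, and the only ORR the Master Protocol quotes for it is about 24%. The 12% belongs to a regimen that is not the Track 1 control. On a quick reading, 5% is the chance that an arm no better than the control reaches the efficacy boundary. At 24% that chance is more than three times as large, and about half of such arms would pass Stage 1.

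If the 5% were read that way, an arm reaching 16/54 could be taken as better than nivolumab plus ipilimumab on weak evidence. Because the primary objective refers to that regimen, the reading is a natural one.

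**Working it through.** **Inputs.** Stage 1 has n1 = 19 and stops at r1 = 4 or fewer responses. The total is n = 54, with futility at r = 15 or fewer (Table 10.1-1 and Section 10.1.1). Stage 2 therefore adds 54 − 19 = 35. The null is 20% and the target 40%. The control regimen's quoted ORR is about 24% (Sections 3.2.1 and 10.1).

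**Formulas**, for a true ORR p:

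- Stage 1 stop: PET(p) = P(Bin(19, p) ≤ 4)
- Boundary crossed: C(p) = Σ over x = 5 to 19 of P(Bin(19, p) = x) × P(Bin(35, p) ≥ 16 − x)
- Expected n: 19 + (1 − PET) × 35
- Stage 1 stop never followed: P(Bin(54, p) ≥ 16)

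**Step 1: reproduce the plan.**

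| True ORR | Stage 1 stop | Crossed | Expected n | Plan prints |
|---|---|---|---|---|
| 20% | 67.3% | 4.8% | 30.4 | 67%, 5%, 30.4 |
| 25% | 46.5% | 21.6% | 37.7 | 21% |
| 30% | 28.2% | 49.7% | 44.1 | 49% |
| 35% | 15.0% | 75.5% | 48.8 | 75% |
| 40% | 7.0% | 90.4% | 51.6 | 90%, 51.6 |

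All agree, allowing for truncation. A search over designs with n up to 60 (error at most 5%, power at least 90%) returns the same optimal design, 4/19 and 15/54.

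**Step 2: at and around the control regimen's quoted rate.** The documents give neither a sample size nor an interval for the 24%, so 22% to 26% is an assumed range, not a confidence interval.

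| True ORR | Stage 1 stop | Crossed, stop followed | Crossed, stop ignored | Expected n |
|---|---|---|---|---|
| 20% | 67.3% | 4.8% | 6.0% | 30.4 |
| 22% | 59.0% | 9.7% | 11.9% | 33.3 |
| 24% | 50.6% | 17.1% | 20.6% | 36.3 |
| 26% | 42.6% | 26.7% | 31.8% | 39.1 |

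At 24% the ratio to the 20% figure is 17.1/4.8, about 3.5. The 17.1% lies between the plan's own 5% at 20% and 21% at 25%.

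**Step 3: below 20%.** Crossing falls to 2.0% at a true ORR of 18% and 0.4% at 15%. The error is therefore at most 5% at every true ORR up to 20%, and the plan's description of an arm no better than 20% is accurate.

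**Step 4: what crossing shows about 24%.** The exact 90% Clopper-Pearson interval at 16/54 is 19.6% to 41.5% (the plan prints 19% to 42%). The lower limits at 17, 18 and 19 of 54 are 21.2%, 22.8% and 24.4%. With 16 to 18 responses, 24% is not excluded; from 19 it is, at this level. At a true ORR of 40%, the chance of passing Stage 1 and reaching at least 19/54 is 77.8%, so 77.8/90.4 = 86% of crossings clear 24%.

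**Step 5: the cost of raising the null.** Keep 19 and 54 participants and the Stage 1 rule. The lowest final cut-off with error below 5% at 24% is then 19/54 (error 4.0%; 18/54 gives 7.0%). Power at 40% drops from 90.4% to 77.8%.

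**The case for a change.** The strongest case for a change is that the label and the number do not match. The plan names a control, quotes about 24% for it, then calls 20% the historical control without explaining the step. The Track 2 text, by contrast, says openly that its 5% null is a judgement about what is worth studying. The 21% at a true ORR of 25% is presented as power, so nothing tells the reader that 25% is close to the control regimen's own quoted rate. Even at 22% the crossing probability is about twice the nominal 5%. One relabelled phrase and a few sentences would cost almost nothing.

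The missing rationale and the loose label stand as observations. The rest does not amount to a defect:

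- Historical rate is the usual name for a Simon null. Here it matches the table's column heading, is given explicitly as 20%, and is said to rest on both the 24% and the 12%. The plan nowhere says the 5% protects against an arm equal to the concurrent control, or that 16/54 shows superiority to it.
- Section 10.3.1 assigns that comparison to the randomized arms, with an odds ratio, an ORR difference and hazard ratios, each with a 95% confidence interval. Section 10.1 brings relative arm performance into the decision.
- The 24% is itself approximate. Section 3.2.1 describes GC or GEJ participants, whereas eligibility reads "All participants must have inoperable, advanced, or metastatic EC, GC or GEJ carcinoma". It is no firmer an anchor than 20%.
- The obvious corrective sentences would be inaccurate. Tying the 5% to a true ORR of exactly 20% is wrong (Step 3). Saying that crossing is no evidence of an ORR above 24% fails from 19 responses upward (Step 4).

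**Conclusion.** No change follows. The operating characteristics are correct at the null the plan states. The consequence of a higher control rate can be read from figures already printed: 21% at a true ORR of 25%, and an interval at 16/54 that contains 24%. An analyst who wants the value at 24% can compute 17.1% from the published cut-offs.

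New wording would leave the cut-offs, sample size, power and analyses as they are, so the same arms would cross the boundary. The counts are a guideline and the trial is closing early under Protocol Amendment 06. Raising the null to 24% would be a different design with a real cost in power (Step 5); choosing 20% is a fair trade-off for a signal-seeking phase 2 arm that has a randomized control beside it.

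The 17.1% assumes that the true ORR is 24% and that the Stage 1 stop is followed; it is 20.6% if the stop is always overruled. It is a boundary-crossing rate, not the sponsor's final decision error. Figure 10.1.1-1, the sub-protocols and a separate SAP were not available, and any of them may already give the value near 24% or the reason for choosing 20%.

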### 10.1.1 Track 1 - Anti-PD-1, Anti-PD-L1, and Anti-CTLA-4 Treatment-naïve Participants

As shown in Table 10.1-1, a minimum of 19 participants in each study treatment combination arm will be treated in Stage 1 for an initial evaluation of efficacy. If the total number of responses observed in Stage 1 is  $\leq 4/19$ , the study treatment combination arm would likely not be considered efficacious; otherwise, enrollment to Stage 2 will continue, and an additional 35 participants will be treated. If the total number of responses at the end of Stage 2 is  $\leq 15/54$ , the study treatment combination arm will be terminated for futility; if there are more than 15 responses observed at the end of Stage 2, the study treatment combination arm may be carried on for further treatment development. The totality of efficacy data and response profile for each combination arm will be considered when making decisions to terminate or continue an arm.

The operating characteristics of this Simon 2-stage (optimal) design are provided in Figure 10.1.1-1. With the stopping boundaries as shown in Table 10.1-1, if the study treatment combination arm has an ORR no better than the historical control at 20%, then there is a 95% overall chance of stopping for futility, with a 67% chance of stopping at Stage 1; there is a 5% false positive rate. If the study treatment combination arm has an ORR equal to the target of 40%, then there is a 90% chance of declaring efficacy after Stage 2, whereas if the true ORR is 25%, 30%, or 35%, the power would be 21%, 49%, or 75%, respectively.

**Figure 10.1.1-1: Operating Characteristics of Track 1 Simon 2-stage (Optimal) Design (Power = 90%, Alpha = 5%)**

Abbreviation: prob = probability.

If 16 responses are observed at the end of Stage 2 (Declare Efficacy), then the 90% confidence interval (CI) for ORR will be (19%, 42%). The CI is calculated using the Clopper-Pearson method.

[figure not shown]
As stated in [Section 10.1](#), the number of responses given here is used for sample size calculation and for simplicity of description. Before making a decision to terminate or continue an arm, BMS will also review the totality of all available data, which includes other aspects of efficacy that may help predict OS benefit, such as DOR and PFSR; clinical safety information; and biomarker data, as well as the relative performance of other treatment arms.

### **10.1.2 Track 2 - Anti-PD-1, Anti-PD-L1, or Anti-CTLA-4 Treatment-experienced Participants**

For each study treatment combination arm under Track 2, the Simon 2-stage (optimal) design will be used. Initially, 21 participants per study treatment combination arm will be treated in Stage 1 and preliminary efficacy will be assessed when those participants are evaluable. If 1 or fewer responses are observed in Stage 1, the study treatment combination arm would likely not be considered efficacious; otherwise, Stage 2 will be initiated and enroll an additional 20 participants, for a total of 41 participants per study treatment combination arm. The totality of efficacy data and response profile for each combination will be considered when making decisions to terminate or continue an arm.

The operating characteristics of this Simon 2-stage (optimal) design are provided in [Figure 10.1.2-1](#). With the stopping boundaries as shown in [Table 10.1-1](#), if the study treatment combination arm has an ORR no better than 5%, then there is a 95% overall chance of stopping for futility, with a 72% chance of stopping at Stage 1; there is a 5% false positive rate. If the study treatment combination arm has an ORR equal to the target of 20%, then it has a 90% chance of declaring efficacy after Stage 2.

**Figure 10.1.2-1: Operating Characteristics of Track 2 Simon 2-stage (Optimal) Design (Power =90%, Alpha = 5%)**

[figure not shown]
Abbreviation: prob = probability.

If 5 responses are observed at the end of Stage 2 (Declare Efficacy), then the 90% CI for ORR will be (5%, 24%). The CI is calculated using the Clopper-Pearson method.

As stated in [Section 10.1](#), the number of responses given here is used for sample size calculation and for simplicity of description. Before making a decision to terminate or continue an arm, BMS will also review the totality of all available data, which includes other aspects of efficacy that may help predict OS benefit, such as DOR and PFSR; clinical safety information; and biomarker data, as well as the relative performance of other treatment arms.

Both participants previously treated in any track (re-randomized participants) and new participants who meet eligibility criteria are permitted to enter Track 2. Some slots in Track 2 will be reserved for re-randomized participants to ensure that both types of participants are enrolled in Track 2. At the initiation of the study, recruitment of re-randomized participants will be limited to 11 participants per Track 2 study treatment combination arm in Stage 1. In Stage 2, recruitment of additional re-randomized participants will be limited to 12 participants out of the 27 additional participants. The limited number of re-randomized participants may be re-adjusted depending on the enrollment rates, the rate of progression in Tracks 1 and 2, and the number of currently open study treatment arms in Track 2.

